### **Setting**

Subjects will be treated with Lunaphil Ultra in one NLF and Juvederm Ultra 4® in the opposite NLF.

A total of 108 participants will be enrolled in the study. For each participant, the products will be injected in the first visit and if needed an additional injection will be done (touch-up) at visit 2 (week 2). The duration of the study is 24 weeks for each participant.

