### ***8.7.2 Main Statistical Methods***

The mean level of improvement from baseline in NLFs severity score based on assessments by evaluating investigators and the injection volume to obtain optimal result will be analyzed using either a paired t-test or a signed-rank test.

The number of patients with an improved score for the PGAIS, proportion of NLFs with clinically significant improvement and the number of NLFs receiving touch-up treatment will be analyzed using a McNemar test.

The safety data will be analyzed primarily using summary statistics. Summary statistics are included the number of subjects (number and percentages) and then classified according to system organ class and preferred term for AEs and SAEs. The incidence of the preferred term for grades 3 and 4 of AEs will be reported. Moreover, causality will be assessed and its results will be reported by frequency and percentage.

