3. The injected volume to obtain optimal aesthetic result (initial treatment + touch-up)
4. The number of NLFs receiving touch-up treatment
5. The incidence, severity and causal relationship of adverse events

Section 3: Research Methods

Study Design

This is a randomized, double-masked, active controlled, within-subject, and equivalency study to compare the effectiveness and safety of Lunaphil Ultra (Hyaluronic acid, produced by Espad Pharmed Co.) versus Juvéderm® Ultra 4 (Hyaluronic acid, produced by Allergan Co.) for the management of moderate or severe NLFs.

Intervention

Subjects will be treated with Juvéderm® Ultra 4 in one NLF and Lunaphil Ultra in the opposite NLF. Two treatments will be allowed over a 2-week period (initial treatment plus one touch-up) to achieve optimal correction of the NLFs. The level of correction will be assessed by the evaluating investigator at week 2 after the initial treatment and, if less than optimal, the treating investigator will be directed to retreat the undercorrected NLF(s).

Randomization

The subjects will be randomized into two possible treatment groups. The first treatment group will receive Lunaphil Ultra on the right side and Juvéderm® Ultra 4 on the left side of their face. The second treatment group will receive Juvéderm® Ultra 4 on the right side and Lunaphil Ultra on the left side of their face. The randomization plan of the subjects will be carried out centrally using an R-CRAN software version 4.0.3. Blocks (with the size of 2) will be made using permuted block randomization for a total of 108 subjects (1:1 allocation ratio).

Blinding

To prevent any bias arising from awareness of face-side allocation, this study will be performed in a double-blind manner. For each participant, one side of the face will receive the investigational hyaluronic acid product and the other side will receive the reference Hyaluronic acid product, according to the pre-specified randomization plan. Both the participants and all investigators responsible for administering injections and assessing outcomes will remain blinded to the allocation throughout the study.

Sample size

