4. Not possible to follow the participant's condition (Loss to follow-up)

5. Change in participant's conditions, which needs change of treatment due to investigator decision or administration of prohibited medications in the protocol

Data sources and measurement

All data will be collected by specialists and recorded in a booklet comprising five visits. Baseline information (demographics, past medical history, history of filler injection, patients' medications), intervention information (e.g., dosage at visit 1 and touch up), WSRS, and PGAIS will be recorded.

All adverse events (AEs) will be documented and categorized according to their frequency, severity (graded using the Common Terminology Criteria for Adverse Events version 5.0) (14), and their assessed causality, following the World Health Organization guidelines (15). The AEs will be reported using the Medical Dictionary for Regulatory Activities (MedDRA) under both the preferred term (PT) and system organ class (SOC) (16). Serious adverse events (SAEs) will be documented in compliance with the E2B(R2) guideline (17) and will be defined as any AE that “results in death, is life-threatening, requires inpatient hospitalization or prolongation of existing hospitalization, results in persistent or significant disability/incapacity, is a congenital anomaly/birth defect, or other medically important condition.”

Section 4: General issues for statistical analysis

Analysis populations

Primary efficacy will be analyzed on a per-protocol population. Also, the primary outcome and secondary key variables of the study will be examined on the intention-to-treat population, and sensitivity analysis will be used to compare the primary outcome in the two populations. All analyzes of complications will be performed based on the safety population.

1. Per-protocol population: all patients who were randomly treated with the study drug and did not have a major deviation from the protocol.
2. Intention-to-treat population: all patients randomly assigned to one of the treatment groups. Patients are analyzed according to the treatment they received randomly.
3. Safety population: All patients who randomly received at least one dose of the study drug. Patients are analyzed according to the treatment they actually received.

Protocol violations and deviations

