Descriptive statistics for baseline characteristics will be presented as mean and standard deviation for continuous variables, and as frequency and percentage for categorical variables.

Section 7: Statistical Analysis

This section describes the planned statistical analyses for efficacy and safety outcomes. Results will be summarized using appropriate descriptive statistics and analyzed using suitable statistical models depending on the data type. Treatment effects will be presented with 95% confidence intervals and two-sided p-values, using a significance level of 0.05.

Primary Endpoint Analysis

For the statistical analysis of the primary outcome (equivalence assessment of the mean level of improvement from baseline in NLFs severity score), both categories of Per-Protocol and Intention-to-Treat statistical population will be examined. Although the main approach is the results of the statistical analysis of the Per-Protocol population, eventually a sensitivity analysis will be performed between the results of the said analysis and the results of the statistical analysis of the Intention-to-Treat population.

Paired t-test or a signed-rank test will be used to compare the mean level of improvement from baseline in NLFs severity score based on assessments by evaluating investigators between Lunaphil Ultra (Hyaluronic acid, produced by Espad Pharmed Co.) compared to Juvéderm® Ultra 4 (Hyaluronic acid, produced by Allergan Co.). The 95% confidence interval (CI) for the mean difference between the two treatments will be calculated. Equivalence will be concluded if the entire 95% CI falls within the pre-specified equivalence margin of ± 0.17 .

Secondary Endpoints Analysis

- The number of patients with improvement score for the PGAIS will be analyzed using a McNemar test.
- The proportion of NLFs maintaining a clinically significant improvement will be analyzed using a McNemar test.
- Injection volume to obtain optimal result will be analyzed with a paired t-test or a signed-rank test.

The number of NLFs receiving touch-up treatment will be analyzed using a McNemar test.

Safety Analysis

All adverse events (AEs) data will be descriptively analyzed. Also, AEs in two groups are compared

using Pearson chi-square test.

The incidence and percentage of treatment-emergent adverse events will be reported, categorized by system organ class (SOC) and preferred term (PT). Adverse events' severity, seriousness, and causality assessment will be reported.

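### The SAP's as-treated safety rule and its two-group adverse event comparison cannot separate the products when every participant receives both

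*SAP*

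**What the plan says.** **Who is in the safety set.** SAP Section 4, Analysis populations, includes "All patients who randomly received at least one dose of the study drug" and adds: "Patients are analyzed according to the treatment they actually received".

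**Exposure.** SAP Section 3, Intervention: "Subjects will be treated with Juvéderm® Ultra 4 in one NLF and Lunaphil Ultra in the opposite NLF". The Setting part of the protocol abstract says the same.

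**What a treatment group is.** SAP Section 3, Randomization: "The subjects will be randomized into two possible treatment groups". These are the two side sequences (Lunaphil Ultra right and comparator left, or the reverse). No other treatment groups are defined.

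**How events are counted and compared.** Protocol 8.7.2 summarises adverse events as "the number of subjects (number and percentages) and then classified according to system organ class and preferred term", without a product or fold dimension. SAP Section 7, Safety Analysis, describes all adverse events, compares them between two groups by Pearson chi-square, and does not say what the groups are.

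**What is recorded for each event.** Protocol 8.4 and 8.5 and SAP Section 3, Data sources and measurement, list MedDRA term and class, CTCAE grade, seriousness, causality and (SAP) frequency. None names a fold, side or product. Protocol Section 10 judges causality against the study treatment as a whole.

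**Scope.** Protocol 8.4 and the SAP Synopsis describe the adverse event outcome as injection site reactions. Protocol Section 6 and SAP Sections 2, 5 and 7 cover adverse events generally.

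**The concern.** Assigning patients to a column by the treatment received is a parallel-group rule. The SAP introduction also calls the trial parallel-group, although its title and design section call it within-subject. In this design the patient is not the unit that receives a product; the fold is. The efficacy endpoints recognise this: clinically significant improvement and touch-up are both counted per fold. The safety analysis does not.

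Safety compared with the reference product is a secondary objective in the SAP Synopsis. As written, the plan does not lead to a product comparison of adverse events, and the analyst would have to invent the attribution rule after the data are in. Local reactions can be attributed to a product only if the side is known. Participants and assessors are blinded, so the route from a reaction to its product is side plus the randomization list, and a side not noted at the visit is hard to recover later.

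**Working it through.** **The plan's own figures.** The documents give no adverse event rate and no power for safety. Their one design calculation reproduces: a paired two one-sided test with SD 0.510, limits ±0.170, true difference 0 and 2.5% per side has power 79.7% at n = 96 and 80.3% at n = 97, and 97 / 0.90 = 107.8, hence 108. It has no bearing on this point.

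**Step 1: try each meaning of the two groups.**

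- *Side sequences.* Every correctly treated participant in either group received both products. The chi-square compares right/left with left/right and contains no product contrast.
- *Products, with the safety-set rule taken literally.* Every correctly treated participant received both, so both columns hold the same patients and events, and the difference is 0.
- *Products, with local events assigned by fold.* This works for local events only, and needs the side. The documents do not say what happens to a non-local event.

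**Step 2: size if non-local events were counted under both products.** Assumptions, not document figures: local reactions on a proportion p1 or p2 of folds, and a proportion q of participants with a non-local event, independent of local reactions.

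- Pooled incidence for a product = 1 − (1 − p)(1 − q)
- Pooled difference = (1 − q)(p1 − p2)

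With p1 = 0.30, p2 = 0.20, q = 0.15: 1 − 0.70 × 0.85 = 0.405 and 1 − 0.80 × 0.85 = 0.320. The difference is 0.085 and the ratio 0.405 / 0.320 = 1.27, against 0.10 and 1.50 for local reactions alone. Across a range, from the same formulas:

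| q | 30% v 20%: pooled | Difference (points) | Ratio | 30% v 15%: pooled | Difference (points) | Ratio |
|---|---|---|---|---|---|---|
| 0 | 30.0 v 20.0 | 10.0 | 1.50 | 30.0 v 15.0 | 15.0 | 2.00 |
| 10% | 37.0 v 28.0 | 9.0 | 1.32 | 37.0 v 23.5 | 13.5 | 1.57 |
| 15% | 40.5 v 32.0 | 8.5 | 1.27 | 40.5 v 27.8 | 12.8 | 1.46 |
| 20% | 44.0 v 36.0 | 8.0 | 1.22 | 44.0 v 32.0 | 12.0 | 1.38 |
| 30% | 51.0 v 44.0 | 7.0 | 1.16 | 51.0 v 40.5 | 10.5 | 1.26 |
| 50% | 65.0 v 60.0 | 5.0 | 1.08 | 65.0 v 57.5 | 7.5 | 1.13 |

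The row q = 0 is also the result for any single local preferred term: non-local events carry other terms and do not enter it.

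**Step 3: what a count of subjects can show about local reactions.** With 30% and 20% of folds affected, independently between folds, the proportion of participants with at least one reaction is 1 − 0.70 × 0.80 = 0.44. Equal rates of 25.2% on each side give the same figure, since (1 − 0.252)² = 0.56. Without the side, the two situations cannot be told apart.

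**Step 4: pairing.** If the columns are products, each participant contributes to both, and an unpaired chi-square ignores this. In a simulation of 108 pairs (5,000 runs, 20% v 20%, no non-local events), its type I error was 5.7%, 2.0% and 0.3% at latent between-fold correlations of 0, 0.5 and 0.8. A paired test corrects that, but it still needs each event assigned to a fold.

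**The case against.** - **No passage files non-local events under both products.** This stands. A reader might infer that double counting is the plan's rule, but the documents are silent. The protocol's count of subjects by class and term, with no product column, is compatible with counting such an event once.
- **Any dilution is limited.** This stands. A reader might infer that every safety difference is diluted. Only pooled any-event totals, or class totals mixing local and non-local terms, would be affected. If the analysis were confined to injection site reactions, dilution would disappear, but the need for the side would remain.
- **A missing fold item does not affect non-local events.** This stands. They have no fold. The missing item and the missing counting rule are two separate gaps.
- **Silence in the text is weak evidence about the booklet.** This stands. The same lists name WSRS, PGAIS and injected amount without a side, although the paired analyses need all three by fold. One can say only that the protocol and SAP do not state the item.
- **The safety-set sentence may be the usual provision for treatment errors.** This stands in part. It is a reasonable intention, but at patient level it does not work: a participant whose sides were swapped still received both products. The rule has content only at fold level.
- **Safety has no equivalence test.** This stands. A reader might infer a bias towards an equivalence conclusion, but the ±0.17 margin applies to WSRS only.
- **Both products are not always injected together.** This stands in part. A touch-up may treat one fold. Both products are already in place by then, so a non-local event still cannot in general be attributed to one of them.

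**Conclusion.** The point holds as a gap between a stated rule and the design. The patient-level safety rule and the undefined two-group comparison cannot produce a product contrast when each participant receives both products: the sequence reading contains none, and the literal product reading gives identical columns. This follows from the documents and needs no assumed rate.

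The effect of double counting is conditional. With local reactions on 30% v 20% of folds and 15% non-local events, a pooled difference falls from 10 to 8.5 points and the ratio from 1.50 to 1.27; over q from 10% to 50% the difference runs from 9.0 to 5.0 points. This rests on assumed rates, independence, and a counting rule that the plan does not state.

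The absence of a fold or side item matters for local injection site reactions and is a finding about the protocol and SAP text, not the booklet. The primary endpoint is unaffected. The change should be made because the comparative safety objective cannot be met as the analysis is written.

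**What to change.** 1. In SAP Section 4, replace the last sentence of the safety population with: *folds are analysed according to the product actually injected in that fold*.
2. In protocol 8.5 and SAP Section 3, state that side is recorded for each adverse event (right / left / both / not local). If the booklet lacks the item, add it.
3. In SAP Section 7, define the product comparison as local reactions per fold, by product injected, with a method that respects the pairing.
4. In SAP Section 7 and protocol 8.7.2, tabulate non-local events and serious adverse events once per participant, without a between-product comparison.

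The cost is a few sentences and at most one tick-box. The small downside is that non-local events leave the product comparison, where they could not in general be attributed to one product.

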In an equivalence test of means using two one-sided tests on data from a paired design, a sample size of 97 achieved 80% power at a 2.5% significance level. When the true difference between the means was 0.000, the standard deviation of the paired differences was 0.510, and the equivalence limits were -0.170 and 0.170. Considering a drop-out rate of 10%, total sample size required is 108.

Study Population Criteria

Inclusion Criteria

1. Subjects \geq 30 years of age

2. Visible bilateral NLFs that are approximately symmetrical and have an equal severity ranging from moderate to severe (assessed at the deepest part)
3. Able to follow study instructions and likely to complete all required visits
4. Signed informed consent

Exclusion Criteria

1. History of bleeding disorders or participants receiving or recently exposed (≤ 3 weeks) to continuous treatment with thrombolytics, anticoagulants, platelet inhibitors, or NSAIDs
2. Acute herpetic eruption
3. Known susceptibility to keloid formation, hypertrophic scarring or clinically significant skin pigmentation disorders
4. Known sensitivity to local anesthetics of the amide type (such as lidocaine), history of hypersensitivity to gram-positive bacterial proteins, history of multiple severe allergies, history of anaphylactic shock
5. Known hypersensitivity to any component of the study products or excipients (like hyaluronic acid)
6. History of receiving immune therapy or a history of autoimmune disease
7. History of active chronic debilitating systemic disease
8. History of connective tissue disease, history of malignancy (except for non-melanoma skin cancer) within the last 5 years
9. Clinically significant active dermatologic disorders within the last 6 months
10. Use of oral retinoids, OTC or prescription antiwrinkle treatments, microdermabrasion, or chemical peels in the NLF area within the last 4 weeks or intention to use them during the study
11. Any prior cosmetic procedure or tissue augmentation at the NLF injection site within 1 year before study entry (or intent to undergo such a procedure during the study)
12. Pregnancy or breastfeeding

Withdrawal Criteria

1. Withdrawal of consent by the participant
2. Noncompliance, including refusal of study medical requirements, refusal of procedures as stated in the study protocol, or use of prohibited medications
3. The occurrence of an undesirable event that causes the investigator to consider the participant's exclusion from the study

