A protocol deviation refers to any change, non-compliance, or departure from the approved protocol such as enrolling a participant who did not meet all the inclusion/exclusion criteria, visit non-compliance, incorrect execution of the consent form, participant declines to complete scheduled research activities, use of unapproved recruitment procedures, use of an unapproved version of the Participant Information and Consent Form, dispensing or dosing error for study medication/drug, and any change, divergence, or departure from the study design or procedures defined in the protocol. The per-protocol (PP) population is a subset of the Intention-To-Treat (ITT) population, which includes participants who completed the study without any major violations of the protocol. Description of which protocol deviations will be summarized. No participants will be excluded from the ITT analyses due to protocol deviations.

Statistical Software

The analysis will be carried out using Stata (StataCorp LP, USA) and R statistical software.

Missing Data

The missing WSRS scores at week 24 for participants with available week 12 data will be imputed based on their WSRS scores at week 12. For participants with missing WSRS scores at week 12, no imputation will be performed. In the ITT population, imputation for this outcome will be conducted as described above.

Outlier data

Outliers are identified by examining standard charts, and those that are visually "distinct" are evaluated to check the impact on the results by comparing the results of the analysis with and without outliers.

Data Transformations

No transformations of raw data are planned prior to statistical analysis. All variables will be analyzed using their original measurement scales, unless transformation is deemed necessary during model diagnostics. In such cases, justification and details will be documented in the statistical outputs and Clinical Study Report (CSR).

Multiple comparisons and multiplicity

No formal procedures for multiplicity adjustment are planned for this study, as the study was not designed to perform multiple statistical comparisons for primary or key secondary endpoints. Therefore, the overall Type I error rate will not be adjusted.

Covariate Adjustment

No covariate adjustment will be done.

Planned subgroup analysis

No subgroup analysis will be done.

Section 5: Outcome Variables

Primary Outcomes

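### The SAP's ITT check is an available-case analysis that omits the same early leavers as per-protocol, so agreement between the two says nothing about them

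*SAP*

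**What the plan says.** SAP Section 4, Analysis populations, makes per-protocol the primary efficacy set and gives the other set as "Intention-to-treat population: all patients randomly assigned to one of the treatment groups". The primary outcome is then compared between the two sets as a sensitivity analysis. Under Protocol violations and deviations the SAP adds "No participants will be excluded from the ITT analyses due to protocol deviations", and describes per-protocol as participants who finished the study with no major violation.

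Under Missing Data, a missing week-24 WSRS is imputed from week 12 where week 12 exists. Otherwise: "For participants with missing WSRS scores at week 12, no imputation will be performed". The section closes by applying the same rule to ITT.

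SAP Section 7, Primary Endpoint Analysis, uses a paired t-test or signed-rank test. Equivalence is declared when the whole 95% CI lies inside ±0.17. Neither the SAP nor protocol section 8.7 gives a repeated-measures model, multiple imputation or a tipping-point analysis.

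On size, SAP Section 3 and protocol section 8.6 agree: "a sample size of 97 achieved 80% power at a 2.5% significance level", and then "Considering a drop-out rate of 10%, total sample size required is 108".

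**The concern.** The primary endpoint needs a week-24 score on both folds. Someone who leaves after week 12 is scored from week 12. Someone who leaves before week 12 and does not return has nothing at either visit, so no paired difference exists and the paired test drops them. The set analysed is then smaller than the set defined.

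The same people are missing from per-protocol, whether it is read as completers only or as treated patients without a major deviation, because they have no week-24 score in either case. ITT is the only planned analysis that could have brought them in; the with-and-without-outliers comparison works only on pairs that already have scores. If per-protocol and ITT agree, a reader will take the equivalence claim as robust to drop-out. For early drop-out, that has not been tested.

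**Working it through.** **Inputs.** From SAP Section 3 and protocol section 8.6: "When the true difference between the means was 0.000", "the standard deviation of the paired differences was 0.510", "the equivalence limits were -0.170 and 0.170", 2.5% for each one-sided test, 97 evaluable pairs, 10% drop-out, 108 in total. The documents do not say how many leave before week 12. I assume k = 3, 5 or 11, where 11 is the whole planned loss.

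**The plan's own figure.** Exact power of the paired two one-sided tests (SD 0.51, margin 0.17, true difference 0) is 0.797 at n = 96 and 0.803 at n = 97. Then 97/0.9 = 107.8, rounded up to 108, and 108 − 97 = 11. The stated size reproduces.

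**What the ITT interval rests on if all 11 leave early.** Half-width = t(0.975, 96) × 0.51/√97 = 1.985 × 0.51/9.849 = 0.103. Equivalence is declared when the observed mean difference is within 0.170 − 0.103 = 0.067 of zero.

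**Tipping points.** Let d be the observed mean in the 108 − k scored pairs and x the mean in the k unscored pairs, both groups with SD 0.51 and the unscored pairs treated as if observed.

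- Mean over all 108: M = [(108 − k)d + kx]/108
- Variance: S² = [(107 − k)·0.51² + (k − 1)·0.51² + (108 − k)(d − M)² + k(x − M)²]/107
- Upper limit: M + 1.982·S/√108. Solve for x where this equals 0.17.

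Example, k = 11 and d = 0.05: at x = 0.269, M = (4.85 + 2.96)/108 = 0.0723, S = 0.512, and the upper limit is 0.0723 + 0.0977 = 0.170.

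| Unscored | d = 0 | d = 0.03 | d = 0.05 |
|---|---|---|---|
| 11 | 0.65 | 0.43 | 0.27 |
| 5 | 1.30 | 0.85 | 0.51 |
| 3 | 1.98 | 1.30 | 0.79 |

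Entries are the leavers' mean difference, in WSRS points, that reverses the conclusion. Holding S at 0.51 gives somewhat larger values: 0.71, 0.45 and 0.27 for 11 leavers; 1.57, 0.95 and 0.54 for 5.

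**False equivalence.** Put the true mean over all 108 at 0.17, so that declaring equivalence is an error with nominal rate 2.5%. The scored pairs then have true mean (108 × 0.17 − kx)/(108 − k). For k = 11 and x = 0.5 this is (18.36 − 5.5)/97 = 0.133. The chance that the 95% CI lies inside ±0.17 is:

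| Leavers' mean x | k = 11: scored mean | k = 11: rate | k = 5: scored mean | k = 5: rate |
|---|---|---|---|---|
| 0 | 0.189 | 1.0% | 0.178 | 1.7% |
| 0.17 | 0.170 | 2.5% | 0.170 | 2.5% |
| 0.5 | 0.133 | 10.7% | 0.154 | 5.0% |

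These are exact calculations. Simulation of the x = 0.5 row gives 10.8% and 4.9%, the same within simulation error.

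**The case against.** The best defence is that this touches a supporting analysis, for a number of people that may be very small, in a design that limits the harm. Each participant carries both products, so a leaver removes a whole pair and cannot unbalance the arms. Someone unhappy with one fold may be unhappy with either product. If 11 leavers split 6 to 5 at +1 and −1 point and d = 0.05, the upper limit over all 108 is 0.165, still inside the margin. At the plan's own assumption of no difference, reversal needs leavers to average 0.65 points even if all 11 go early. SAP Section 6, Participant flow, also promises discontinuations with reasons and the number in each set. All of this stands. It limits the size of the problem, but disclosing the losses does not analyse them.

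Several stronger readings are tempting and are not supported:

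- **That the omission biases towards equivalence.** It does so only if leavers' differences lean the same way as any true difference and by more than in those who stay. If leavers average 0, false equivalence falls below 2.5%.
- **That the ITT analysis cannot be run.** It can; it is a well-defined available-case analysis under the wrong name.
- **That the rule breaks the bar on exclusions for deviations.** Having no outcome value is a different reason for not contributing. The clash is with the ITT definition.
- **That everyone who misses week 12 is lost.** Someone who misses week 12 but attends week 24 keeps the observed score. Only those missing both drop out.
- **That usable data exist on most early leavers.** Both schedules score WSRS at the two-week visit, but nothing says how many leavers reach it, and that score precedes any touch-up.

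**Conclusion.** The point holds as a labelling and sensitivity gap. The ITT definition and the missing-data rule do not describe the same set, nothing else in the documents reconciles them, and the planned comparison cannot show what early leavers would do to the result.

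How much this matters depends on two quantities the documents do not give: how many leave before week 12, and their mean between-product difference. If early leavers resemble the rest, the error rate stays at 2.5%. The rate near 11% needs both the full drop-out allowance lost early and a mean difference almost three times the margin (0.5/0.17 = 2.9). The conclusion is most fragile when the observed difference is already near the 0.067 pass limit: at 0.05, 11 leavers averaging 0.27, or 5 averaging 0.51, reverse it. With few leavers and an observed difference near zero, reversal is hard to imagine. The change should be made, but the documents give no basis for saying that the trial will reach a wrong conclusion.

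**What to change.** In SAP Section 4, Missing Data:

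1. Describe the current analysis as participants with an observed or week-12-imputed week-24 WSRS, do not call it ITT, and report how many randomised participants it omits.
2. For the ITT primary analysis, add a tipping-point table over all randomised participants. For those with no week-24 value, shift the between-fold difference in improvement (Lunaphil Ultra minus Juvéderm Ultra 4) in steps up to 1 point in each direction. Report where the 95% CI crosses ±0.17, or that it does not cross in that range.
3. Optionally, add a repeated-measures model of the within-participant difference over the post-injection visits, so that earlier scores contribute. State that it assumes missing at random and that two-week scores precede any touch-up. It does not replace the table.

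Do not carry baseline forward. Eligibility requires equal severity on both sides, so this would impute a zero difference and pull the result towards equivalence. With 11 leavers and d = 0.067, the upper limit would fall from 0.170 to 0.152.

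While editing, confirm the week-12 visit on which the rule depends. The SAP timeline shows Visit 3 at 12 weeks; the protocol timeline in section 8.3 reads as 4 weeks in the text available to me, which may only be a broken table.

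The cost is a few lines of SAP text and a little programming, with no new visits, patients or data. The supporting result may look less favourable than under the current rule.
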